The Nephrotic Syndrome Study Network (NEPTUNE) has been created and charged with the purpose of accomplishing the specified study goals. NEPTUNE is comprised of individuals with outstanding dedication and multi-disciplinary investigative expertise. NEPTUNE came into being in large part due to the unflinching support, and significant commitment from the NephCure Kidney International, previously known as The NephCure Foundation, which is a lay research non-profit foundation devoted to understanding and improving the treatment of FSGS. NEPTUNE will operate in full with NephCure. The Halpin Foundation is also a lay research foundation that is supportive, committed and fully engaged with NEPTUNE. NEPTUNE was initially funded primarily through a 5-year grant award (U54 DK083912) from the NIDDK and ORD (\$6.25 million) with additional funding from NephCure (\$2.0 million) and the Regents of the University of Michigan (\$2.0 million). It has received a subsequent 5 year grant award (U52 DK083912-06) from the NIDDK (\$5.81 millions) and the Regents of The University of Michigan (\$4.2 million).

1.C. Specific Aims – Cohort A (Biopsy Group)

Participants presenting with Nephrotic Syndrome will be initially enrolled into two main concurrent cohort studies, namely the FSGS/MCD Cohort Study and the MN Cohort Study. The specific aims and research hypotheses of each of the main cohort studies and the combined cohort are outlined below.

1.C.1. Aims Related to FSGS and MCD

Specific Aim 1: To determine the rates and predictors of clinical remission of FSGS/MCD.

Hypothesis 1: After accounting for the types, duration, and frequency of immunomodulating therapy, the probability of remission of FSGS/MCD defined as change in urinary protein excretion and/or renal function

will be predicted by baseline demographic, clinical, genetic and histopathological characteristics at the time of presentation.

Specific Aim 2: To identify gene expression profiles from renal biopsies of participants with FSGS/MCD that can be used to classify participants into distinct molecular subgroups.

Hypothesis 2: Genome-wide molecular profiles obtained from renal biopsy tissue at the time of diagnosis of FSGS/MCD will independently predict the rate of remission of FSGS/MCD defined as change in urinary protein excretion and change in renal function.

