Specific Aim 3: To identify the transcriptional networks that are associated with individual genetic causes of FSGS/MCD; namely, mutations in *NPHS1*, *NPHS2*, *LAMB2*, *PLCE1/NPHS3* and *WT1*.

Hypothesis 3: Individual genetic causes of FSGS/MCD activate specific transcriptional pathways in renal tissue and the molecular characterization of these transcriptional pathways may serve as novel therapeutic targets with a high likelihood of more complete and sustained remission of FSGS/MCD.

1.C.2. Aims Related to MN

Specific Aim 4: To determine the rates and predictors of clinical remission of MN.

Hypothesis 4: After accounting for the types, duration, and frequency of immunomodulating therapy, the probability of remission of MN, defined as change in urinary protein excretion and/or renal function, will be predicted by baseline demographic, clinical, genetic and histopathological characteristics at the time of presentation.

Specific Aim 5: To identify gene expression profiles from renal biopsies of participants with MN that can be used to classify participants into distinct molecular subgroups.

Hypothesis 5: Genome-wide molecular profiles obtained from renal biopsy tissue at the time of diagnosis of MN will independently predict the rate of remission of MN defined as change in urinary protein excretion and/or renal function.

1.C.3. Aims Related to the Combined Histopathology Cohorts (FSGS, MCD, MN)

Specific Aim 6: To determine the effect of adjuvant (non-immunomodulating) therapy on the clinical remission of Nephrotic Syndrome.

Hypothesis 6: The use of non-immunomodulating therapy (including antihypertensives, lipid lowering, antithrombotic agents and dietary manipulation) will have an independent effect on the probability of remission of Nephrotic Syndrome defined as change in urinary protein excretion and/or renal function.

Specific Aim 7: To determine the rates of major medical complications in patients treated for Nephrotic Syndrome.

Hypothesis 7: The composite rates of major medical complications (vascular thrombosis, complications of kidney biopsy procedure, infection, and death) will vary according to the baseline characteristics and the types of treatment in patients with Nephrotic Syndrome.

Specific Aim 8: To evaluate the quality of life and its trends in participants undergoing treatment for Nephrotic Syndrome.

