Additional factors considered to be associated with outcomes specific to the MN cohort are heavy metal exposures, chronic infections and malignancies. In preliminary unpublished data obtained at the University of North Carolina Kidney Center a trend for a higher frequency of any type of infection in the year prior to MN disease onset compared to those with other glomerular diseases was observed. Oral infections, but not UTI or sinus infections were associated with MN. Two or more years of occupational heavy metal exposure was also highly associated with development of MN. These results indicate that a broader range of infections than originally thought may be associated with MN and that exposure to heavy metals may also play an important role in developing MN. However, the influence of these exposures on disease presentation and outcomes is not known. Data will be collected and analyses (pending additional funding) will be performed on all study cohorts with respect to these considerations.

Response Measurements: The best accepted responses are improved renal survival and complete remission (CR) of proteinuria. About 30% of MN cases will relapse subsequent to a CR (66). The great majority who do, however, will relapse to sub-nephrotic range of proteinuria, and will have stable long-term function. More recently partial remission (PR) has been also recognized as a positive outcome. A recent review on the 350 nephrotic patients with MN found that the 10-year renal survival was 100% in the CR group, 90% in the PR group, and 45% in the no remission group (67). Patients in CR or PR have a similar rate of decline: -1.5 ml/min/year in the CR group and -2 ml/min/year in the PR group. In contrast, the no remission group lost GFR at a rate of -10 ml/min/year. Thus, both CR and PR appear to be excellent predictors of long-term renal survival. In the two largest studies of patients with MN who achieved CR, only a few developed mild renal insufficiency, over a long observation period, and none progressed to ESRD.

2.B. Significance of Proposed Research

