missed data points, in part because the participation time is not appropriately weighted. For these reasons, time to ESRD provides a secondary outcome that obviates most of the problems inherent in a slope-based analysis. Time to ESRD or 50% decline in baseline GFR or 25 ml/min/1.73m² decline in baseline GFR is particularly attractive as a secondary outcome for the FSGS/MCD study because, in general, time to a specified event constitutes a clearer outcome than a slope. In addition, time to event analysis does not force a functional form (i.e. linear decline) on the process of progression. It is likely that the analytic problems associated with a particular measurement technique are minimized when comparing values for an individual over time. Censoring methods are readily applicable to participants who depart early. Lastly, time to ESRD (i.e. initiation of renal replacement therapy for usual clinical indications) is the most important clinical and economic consequence of FSGS/MCD and MN. This time can be ascertained for participants even after formal completion of the proposed study.

3.E.2. Secondary Outcome Variables

Composite of the following events will be considered as secondary outcomes of the NEPTUNE main cohort study. Additional CRFs or appropriate source documentation may be required for further clarification and/or event adjudication for the following ‘secondary outcomes of special interest’:

- (1) Quality of Life: Patient-reported outcome will be assessed using the Patient Reported Outcome Measurement Information System (PROMIS) from ages 8 and above and parent proxy PROMIS measures will be completed for ages 0-10. Overlap in ages 8 to 10 years allows the complete ascertainment of this assessment in children who may find self-reporting difficult due to delayed reading skills.
- (2) New Onset Diabetes: New-onset diabetes is a diagnosis of diabetes as indicated by one or more of the following that was not present at the time of NEPTUNE enrollment.
 - a) Documented diagnosis of diabetes in the medical record
 - b) Casual (non-fasting) blood glucose > 200 mg/dL
 - c) Fasting blood glucose > 126 mg/dL
 - d) 2 hour glucose > 200 after oral glucose tolerance test
 - e) chronic use (> 6 months) of hypoglycemic therapy outside of pregnancy
 - f) Hemoglobin A1C \geq 6.5% (94)
- (3) Malignancies: Any cancer diagnosis of the skin, hematopoietic system, or solid organ after enrollment in NEPTUNE

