We plan to use standard descriptive statistics to characterize the overall study population and subgroups of interest both at baseline and during follow-up. Summary statistics such as means, medians, standard deviations, and ranges will be produced for measured variables. Frequencies will be tabulated for categorical and ordinal variables. Graphical methods will be used extensively to examine distributions, identify potential influential points, and guide in data transformations if warranted. For outcomes collected longitudinally, and to examine associations among various measures, scatterplots and grouped boxplots will be produced to examine assumptions of linearity, symmetry, and homoscedasticity. We can also easily calculate the rate and adjusted hazard rate of the main two clinical outcomes (change in UPE and renal function) using regression methods.

3.F.2. Analysis During the Adaptive Recruitment Phase

The study has several recruitment goals regarding the distribution of various groups, including the distribution of serum creatinine or eGFR, age and other characteristics. At some clinical centers, these measures will be available in advance from automated electronic databases; at others, the data will be available only at the time of the initial clinic visit.

In the sections above, we specified recruitment targets by histological diagnosis. During the course of recruitment, we will examine repeatedly these characteristics by center using the web-based, real-time monitoring function of NEPTUNELink. If, after completion of the recruitment of 300 participants, the distributions of these variables are close to the target ranges specified above, recruitment will be continued as previously described. If not, participants with some levels of these variables were oversampled and others undersampled and corrective measures will be taken to ensure adequate representation of both cohorts. Related statistical analysis will account for this unbalanced sampling through appropriate weighting schemes.

During the protocol revision for Version 3.0, the DACC regarded the number of diagnoses entered into the OG Cohort (Other Glomerulopathies) to be higher than anticipated. In an effort to maintain statistical power for the cohorts of interest (FSGS/MCD and MN) for the study's goals, the overall recruitment target goal was adjusted to 600 to reach the projected targets of 250 and 200 for the FSGS/MCD and MN cohorts, respectively.

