The statistical power calculations are based on the following assumptions. We conservatively assume a loss of 10% of the available follow-up due to participant retention issues. We assume a power of 80%, an alpha of 0.05, an intra-cluster correlation of 0.05, and a between-facility normalized standard deviation of the sample size of 0.15.

Power was computed for a range of sample sizes, event rates, and exposure percentages, representing between- and within-group comparisons and outcomes as described within each aim (Table H). For example, the 50% v. 50% exposure would correspond to an analysis across the entire sample between participants above v. below the median of a continuous covariate. Other percentages correspond to group comparisons of specific biomarker samples or among specific populations (e.g. participants with specified biomarkers, functionally defined subgroups). In each row, the minimum detectable odds ratio (MDOR) using logistics regression is provided with a varying outcome prevalence.

Exposure Percentages		Logistic analyses	
Group A	Group B	Outcome Prevalence	MDOR
50%	50%	35%-45%	2.3
		20%	2.7
20%	80%	35%-45%	2.8
		20%	3.1
20%	40%	35%-45%	3.1
		20%	3.6
10%	50%	35%-45%	6.4-6.9
		20%	6.7

3.F.5.e. Time to Event Analyses

Cox regression will be applied to analyze the time to event data of the primary or secondary endpoints collected in both cohort studies. This analysis allows us to assess association of the disease hazard rate with either clinical covariates of interest or genetic signature panels. Moreover, a survival distribution function of emission or that of renal function loss can be estimated under different patient profiles. A possible complication in the analysis is that patients may experience recurrences of remission, partial remission or no remission during the follow-up period. Thus, it is also of interest to perform an analysis of recurrent event history data, and to compare the results with those obtained from the only endpoint-based time to event analysis.

3.F.6. Data Management Infrastructure

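### The Cox survival function of remission in Section 3.F.5.e has no stated treatment of death or ESRD before remission; if those participants are censored, the absolute probability of remission is overstated

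*Protocol*

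**What the plan says.** Specific Aims 1 and 4 (Protocol Sections 1.C.1 and 1.C.2) call for remission rates as well as predictors: "To determine the rates and predictors of clinical remission of FSGS/MCD" and "To determine the rates and predictors of clinical remission of MN".

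Section 3.F.5.e sets the time-to-event method: "Cox regression will be applied to analyze the time to event data of the primary or secondary endpoints collected in both cohort studies". It then offers an absolute quantity by patient profile: "a survival distribution function of emission or that of renal function loss can be estimated under different patient profiles". It names one difficulty: "A possible complication in the analysis is that patients may experience recurrences of remission, partial remission or no remission during the follow-up period". A recurrent-event analysis is planned for that difficulty, to be compared with the single-endpoint result. Death and ESRD before remission are not mentioned.

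Both events are collected. Section 3.E.2 lists death and ESRD among the secondary outcomes and calls ESRD a final renal outcome. The Protocol's one general remark on censoring, "Censoring methods are readily applicable to participants who depart early", appears in Section 3.E.1.b, in the justification of the renal-function endpoint.

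Section 3.F.1 leaves another route open: "We can also easily calculate the rate and adjusted hazard rate of the main two clinical outcomes (change in UPE and renal function) using regression". Section 3.F.4 makes binary classification of remission against no remission or relapse the primary objective.

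**The concern.** Death ends any chance of remission. Dialysis ends native-kidney remission in practice once no urine ratio can be obtained, because the outcome in Table 3 is a urine protein:creatinine ratio. A single-endpoint survival analysis that censors these participants assumes they would have gone on to remit at the same rate as those still under observation. One minus the resulting curve then describes remission in a population where nobody dies or reaches ESRD, not the proportion who actually remit.

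The Protocol's background suggests that the people affected are concentrated among those still awaiting remission. For MN, Section 2.A.6 reports that "10-year renal survival was 100% in the CR group, 90% in the PR group, and 45% in the no remission group". What is at stake is any profile-specific remission probability the study publishes: the upward bias grows with the competing-event rate, so it differs between the profiles being compared.

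**Working it through.** The Protocol gives no remission rate, competing-event rate or event count for this analysis, so there is no figure of its own to reproduce. The calculation below is an illustration.

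**Inputs**
- Follow-up of 3 years: the 36-month minimum in Section 1.B.
- n = 200 (MN) and 250 (FSGS/MCD): Section 1.B.
- R, the 36-month remission read from the curve with competing events censored: assumed, 30% to 70%.
- c, the combined death/ESRD rate per year: assumed. Section 3.F.5.d gives 0.00 to 0.16 per person-year in children, but that counts 40% eGFR drops as well as ESRD. I therefore treat 0.16 as an upper bound for ESRD in that group. No death rate is given.

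**Formulas** (independent constant hazards)
- Remission hazard: h = −ln(1 − R)/3.
- Cumulative incidence: CIF = h/(h + c) × [1 − exp(−3(h + c))].
- Overstatement = R − CIF; standard error = √(CIF(1 − CIF)/n).

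**One case in full.** R = 50% gives h = 0.693/3 = 0.231. With c = 0.08, CIF = (0.231/0.311) × (1 − e^−0.933) = 0.743 × 0.607 = 45.1%, so the overstatement is 4.9 points.

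**Cumulative incidence, with overstatement in points**

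| R | c = 0.01 | c = 0.02 | c = 0.03 | c = 0.08 | c = 0.16 |
|---|---|---|---|---|---|
| 30% | 29.6% (0.4) | 29.2% (0.8) | 28.8% (1.2) | 26.9% (3.1) | 24.2% (5.8) |
| 50% | 49.3% (0.7) | 48.7% (1.3) | 48.1% (1.9) | 45.1% (4.9) | 40.8% (9.2) |
| 60% | 59.2% (0.8) | 58.5% (1.5) | 57.8% (2.2) | 54.3% (5.7) | 49.4% (10.6) |
| 70% | 69.2% (0.8) | 68.3% (1.7) | 67.5% (2.5) | 63.7% (6.3) | 58.2% (11.8) |

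**Against sampling error**, for R = 50-60% and n = 200-250: 0.37-0.48 standard errors at c = 0.02, 0.55-0.71 at 0.03, and 1.4-1.8 at 0.08.

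**Dependence on the coding rule.** A Kaplan-Meier simulation of 400,000 records at R = 50% and c = 0.16 gives 50.1% when participants are censored at the competing event. It gives 40.9% when they stay in the risk set as non-remitters to 36 months, which matches the cumulative incidence. So the bias comes from the censoring rule, and the Protocol does not state one.

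**Where 0.08 comes from.** A 45% ten-year renal survival corresponds to −ln(0.45)/10 = 0.080 per year if constant. That group was selected on never remitting, so the rate is too high for everyone still awaiting remission. Solving instead for the c that leaves 45% event-free at ten years among never-remitters:
- Remission hazard continuing for ten years: c = 0.026 (R = 50%) or 0.016 (R = 60%); overstatement 1.7 or 1.2 points, 0.35-0.53 standard errors.
- Remission stopping at 36 months: c = 0.071 or 0.068; overstatement 4.4 or 4.9 points, 1.3-1.6 standard errors.

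**Unevenness across profiles** (illustrative). Censored curves of 70% (c = 0.01) and 30% (c = 0.08 to 0.16) differ by 40 points. The cumulative incidences differ by 69.2 − 26.9 = 42.3 to 69.2 − 24.2 = 45.0 points.

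**The case against.** The strongest reply is that the censoring is inferred from silence. Coding of death and dialysis is ordinary SAP content, the SAP is not at hand, and no sentence in the Protocol censors anyone at ESRD in a remission analysis. The remark in Section 3.E.1.b defends time to renal events, where ESRD is itself the event. Section 6.C.8 anticipates continued monitoring, so dialysis participants could be kept as non-remitters, which removes the bias for them. Section 3.E.1 also counts an eGFR at or below 10 as ESRD, and such a participant may still provide urine. The remission curve is offered as something that can be estimated, and Section 3.F.1 allows rates to come from elsewhere.

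Most of this stands and limits the claim. A reader might infer that the Protocol instructs censoring at death or dialysis, or that Aims 1 and 4 are to be answered from this curve alone; the text supports neither. Nor is 0.08 per year a documented competing rate for these cohorts. Section 2.A.6 puts GFR loss without remission at 10 ml/min per year, and Section 3.E.1.a says 5-10 years may be needed to establish loss of function, so early ESRD may be uncommon outside high-risk groups.

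The reply does not remove the point. Continued monitoring cannot apply to the dead, and Section 6.C.8 itself lists events that prevent disease evaluation as grounds for discontinuation. Table 3 defines complete remission by the urine ratio alone, with no native-kidney condition, so even follow-up after transplant needs a rule. Above all, Section 3.F.5.e does more than stay silent: it names a single-endpoint survival function as the route to profile-specific remission, and with competing events censored that function does not give the absolute probability of remission.

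**Conclusion.** The point holds in conditional form. Section 3.F.5.e names a survival function of remission and no treatment of death or ESRD before it. If those participants are censored, one minus that function overstates the absolute 36-month remission probability. Under constant independent hazards and a censored-curve remission of 50-60%, the excess is about 1-2 points at 0.02-0.03 per year and about 5-6 points at 0.08 per year. It is larger in high-risk profiles and negligible where competing events are rare. The remission and competing rates are assumptions, so the true size is unknown.

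A reader might go further and infer that the predictor analyses or the main prediction model are invalid. They are not shown to be: Cox hazard ratios remain interpretable as cause-specific associations, and the binary classification does not use this curve. Nor do the documents establish that contrasts between molecular subgroups will be narrowed; the two-profile example only shows that this can happen.

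**What to change.** Amend Section 3.F.5.e as follows:
- State how death, dialysis and transplant before remission are coded, and which of the two ESRD definitions (Section 3.E.1 or 3.E.2) counts as the competing event.
- Estimate absolute remission probability as cumulative incidence with death and ESRD as competing events: Aalen-Johansen overall, and combined cause-specific Cox models for remission and for death/ESRD where profile-specific curves are wanted.
- Treat death in the same way for the renal-function-loss outcome.
- Keep cause-specific hazard ratios for predictor effects.

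No new data are needed, since death and ESRD are already collected, and standard software suffices. The cost is one further cause-specific model per outcome and slightly lower reported remission probabilities.

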4. HUMAN SUBJECT CONSIDERATIONS

4.A. NEPTUNE Cohort Participant Considerations

4.A.1. Overall Recruitment and Retention Plan

Patients with signs and symptoms of kidney disease consistent with FSGS, MCD, MN or proteinuric renal disease who present for patient care at the participating clinical centers will be the primary study population targeted for enrollment into the NEPTUNE study. The NEPTUNE comprises clinical centers dispersed across the United States of America and the province of Ontario. These clinical centers cover the major population centers in all the regions of the continental US and the largest province in Canada. The volume of new kidney disease patients evaluated and treated annually at the participating clinical centers exceeds 50,000. Specifically, more than 1500 new participants (subjects) who fit the diagnosis of FSGS, MCD, and MN are seen annually at these clinical centers. It is not expected that the volume of activity at these the clinical centers will drop during the recruitment phase for the proposed study. The NEPTUNE team has developed a recruitment plan which entails the following two phases: (1) Pre-screening and identification of potential study participants; (2) Screening and verification of eligibility criteria. Details of these recruitment phases will be outlined in the Manual of Procedures but we hereby provide a brief description of the 4-phase recruitment plan to sufficiently evaluate its soundness. These phases may occur independently and sequentially or simultaneously, to ensure minimal patient burden.

Pre-Screening: The study eligibility criteria are based on current literature and are quite specific to the clinical definition of FSGS/MCD, MN and childhood onset NS. These criteria will be supplemented by manual review of medical records by study personnel who will be centrally and locally trained on recruitment techniques. Dissemination of the study and solicitations to participate in the study will also be facilitated by word of mouth, personal contacts and informational brochures directed to all the physicians in the adult and pediatric nephrology programs of the participating clinical centers and their nephrology referral base. Additional information regarding the study for incident childhood onset NS will be directed toward the Emergency Department and primary care community. The study team member will conduct a checklist assessment of eligibility criteria against the most recent clinical data that is available on the potential participant.

Screening/Verification of Eligibility Criteria: If the participant is deemed potentially eligible by concurrence of a study team member and a physician investigator, the eligibility criteria source documentation form will be initiated without personal health information (PHI). The next step is ascertaining if the potential participant agrees to discuss the NEPTUNE study further with a study team member. Once a potential participant agrees to contact/interaction by a NEPTUNE study team member initial eligibility can be confirmed.

At this visit, the first procedure is to confirm the eligibility criteria with the potential participant and to ascertain willingness to continue with the study process. A physician investigator and/or an experienced study coordinator will then provide all necessary information and a full explanation of the study to the potential participant in accordance with all the requirements of the respective Institutional Review Board and all applicable local, state and federal human participant research regulations. An open, non-coercive dialogue will be conducted with the participant. Patients are considered enrolled and thereby become study participants after a voluntary execution of the IRB-approved written comprehensive consent document. Upon granting of consent, a participant is formally enrolled in the NEPTUNE study and a study number will be assigned. Assent will also be requested from minor participants according to local IRB approved processes and procedures.

4.A.2. Monitoring of Recruitment

The DACC will institute a verifiable process to monitor screening and recruitment at the clinical centers. Timely detection of recruitment deficiency will be a paramount objective of the DACC. Each clinical center will be required to maintain a screening and recruitment log on-site at the clinical center. The recruitment log will also to be used to document the magnitude and reasons for non-participation by eligible patients with a clinical diagnosis of FSGS, MCD, and MN.

Recruitment reports for all the clinical centers will be developed by the DACC for regular review of the Steering Committee and will be included in the progress report to the NIH/NIDDK Project Officer. Monthly recruitment conference calls will be conducted with all the clinical centers in the consortium during which center-specific recruitment obstacles will be discussed together with potential and testable solutions. Recruitment strategies that are effective at one clinical center will be adapted at the other clinical centers whenever such concepts are transplantable.

Data from recruitment logs will be used to construct center-specific graphs of observed and expected recruitment profiles. The recruitment graph is a useful diagnostic tool and an important feedback mechanism that the Steering Committee and DACC will use to develop steps to remedy recruitment deficiency. It is anticipated that all clinical centers will have secured IRB approval by May 1, 2010 and that the training of study personnel at a central location will occur in May 2010.

4.A.2.a. Logistical Considerations

- The complexity of the clinical syndrome that constitutes FSGS, MCD and MN is such that diagnosis and treatment occur within nephrology programs at tertiary academic medical centers. Thus the majority of potential study participants will be efficiently engaged with subspecialty nephrology clinical practices rather than through primary care or other specialty clinics and it is for this reason that the recruitment campaign for this study will be focused on nephrology practices. For the same reasons, we would not use at-large measures such as mass mailing, radio/television announcements, newspaper advertising and screening with serum creatinine measurements at health fairs for recruitment because these are likely to be of low yield.
- Children with incident NS will indeed be identified in the local primary care or emergency department communities. These children are typically referred to pediatric nephrologists for specialty care including initial evaluation, initial treatment and education. This initial identification and referral period will be the focus of eligible pediatric patient identification and screening efforts.
- In order to capture renal biopsy tissue for the cohorts, it is necessary to identify potential study participants prior to the time of a clinically indicated renal biopsy. We propose to use a Forward Operating Study Subject Awareness (FOSSA) System. The FOSSA System entails that study personnel are trained to initiate screening at several points in the healthcare system where the opportunity exists to identify potential study participants. Study personnel screen medical records, appointment schedules and laboratory databases as consistent with local IRB protocols to identify patients who meet any of the following criteria: (1) new onset of proteinuria; (2) new referral with a probable diagnosis of glomerulonephritis and (3) scheduled for kidney biopsy. As part of FOSSA, all major nephrology practices that serve as referral bases for the participating clinical centers will be encouraged to implement the three screening steps of FOSSA with their new patients.
- Each participating clinical center will be required to designate a physician investigator who will be responsible for the recruitment and retention at the clinical centers. The designated investigator and study coordinator responsible for implementing the recruitment protocol will be expected to serve on the study wide recruitment and retention committee.
- The time lost from work, travel and incidental expenses associated with the recruitment and follow-up visits will be reimbursed up to \$100 per participant. Time and effort needed for 24-hour urine collection will be reimbursed at \$50.00 for each satisfactory 24-hour urine collection.
- Several participating clinical centers see a large number of their potential study participants as referrals from significant distances. To accommodate this common scenario and where it is not possible to plan ahead with these participants, they

would be offered an extra day of stay to conduct the study visit and the study would financially bear the necessary per diem expenses.

The NEPTUNE investigators are fully cognizant of the fact that the greatest challenge to the proposed study is the timely attainment of the recruitment goals. Thus, provisions have been made in the budget for a resource intensive recruitment plan and activities. We anticipate significant logistical impediments to achieving the recruitment goals and would deal with these problems expeditiously before the integrity of the study is imminently jeopardized. Unanticipated recruitment problems that are not immediately rectifiable would be met with rapid escalation of alternative strategies.

4.A.2.b. Alternative Recruitment Strategies

- **Additional Clinical Centers:** Three centers in the U.S. (Houston, Winston-Salem and Chicago) have been added to the study network. Academic nephrology programs in these two cities account for hundreds of new FSGS, MCD and MN diagnoses yearly. If proposed recruitment centers falter during the first year, additional clinical centers from large metropolitan areas would be sought to participate in the study. Working relationships currently exist between the proposing teams and the nephrology teams at several large national academic nephrology service providers. These clinical centers are not included in the current application due to limited resources. With unlimited resources, it would have been preferable to blanket recruitment operations across all available centers; however, no study has unlimited resources and operational efficiency and fiscal prudence dictate a plan with the minimum necessary overhead costs should be implemented first. If it becomes necessary to initiate recruitment at these additional clinical centers, resources would be shifted from the non-performing clinical centers originally stated. Clinical centers in Western Europe, Australia and Brazil, as sources of caucasian and black study participants, are also in place as alternative clinical centers that may be called upon to buttress shortfall in the original plan.

4.A.3. Recruitment of Blacks and Pediatric FSGS Patients

Two special populations bear a disproportionate burden with respect to FSGS as reflected in higher prevalence of disease: African Americans (AA) and the pediatric age group. Ideally, a sampling frame in which these two populations are overrepresented in the study cohort will enhance the ability of the proposing teams to test race-specific and pediatric age group-specific research hypotheses. We did not specify oversampling of the AA population because of the success in recruitment of AAs into the initial NEPTUNE cohorts and the large sample size necessary and the limited resources available to expand this to a distribution beyond that representing the racial distribution of individuals with the diseases of interest. A modest size pediatric cohort has been added to NEPTUNE as the cNEPTUNE cohort B which will only include children with incident disease. The study team envisions that future ancillary studies with supplementary recruitment of additional AA and pediatric participants would be pursued if the current proposal is successful in meeting its recruitment target. Notwithstanding this deferment, we would implement several steps to ensure that a significant fraction of the NEPTUNE participants in the current study are of AA race and pediatric age group, respectively. The steps to ensure this objective are: (1) inclusion of several pediatric nephrology programs in the participating clinical centers; (2) inclusion of clinical centers located in cities with two of the three largest AA populations in the US (Detroit and New York). The study team monitors the proportion of AA and pediatric participants enrolled as part of the recruitment monitoring plan and will be prepared to institute additional measures if either of these two important populations are underrepresented in the recruited cohort by study month 10 (one-third of the way through the 30-month recruitment period).

4.B. Retention Plan

In order to protect the power for statistical analyses of main research hypotheses, it would be necessary to maintain a retention rate of >85% by the end of the study. This means that the study cannot afford more than an annual average loss to follow-up rate exceeding 5%. Two periods are most vulnerable to patient dropout. Initially, patients

who have not fully anticipated the effort needed to comply with the study protocol may drop out in their first year of enrollment as the study requirements overwhelm them. Therefore, we implement a “recruit-to-replace” strategy during the entire 30-month recruitment phase to ensure that early attrition does not jeopardize study power. A slightly higher rate of dropout is to be expected in the last two years of the study when many patients become “fatigued” from the protocol requirements, thus an initial recruit-to-replace will also ensure that the study has enough spend down to spare during the last two years of the study. Specific measures that will be taken to enhance retention include: (a) regular contact with referring physician practices; (b) use of trained, certified study personnel to perform study visits and; (c) meeting of investigator with each study participant at least once annually during one of the follow-up visits. Established practices such as mailings and personal telephone calls to remind patients about forthcoming appointments will also be incorporated. The study team will promptly provide results of study tests to referring physicians, pending additional funding. Participants will be encouraged to include family members in their follow-up visits since this may enhance the participant support without extra costs. Follow-up visit appointments will be scheduled with large appointment windows to allow for more flexibility and participants’ convenience.

The prevailing economic downturn coupled with the fact that many participants will be referred to the clinical centers from long distances, leads to an expectation that a significant proportion of the study participants will have fiscal limitations in meeting out-of-pocket travel expenses and in fact their prescribed medications. Studies in more economically advantaged populations also suggest that travel cost is an impediment to participation in clinical research when travel distance to/from the clinic is >100 miles. The NEPTUNE Steering Committee may vote to implement several measures to assist study participants:

